## SYNOPSIS

**TITLE: A phase 2, randomized, double-blind, placebo-controlled study of hesperidin therapy on COVID-19 symptoms:  
The Hesperidin Coronavirus study (Hesperidin)**

**INDICATION:** Reduction of symptoms in patients with COVID-19 infection.

### OBJECTIVES:

- The **primary objective** of the study is to determine the effect of hesperidin therapy on the presence of selected COVID-19 symptoms (fever, cough, shortness of breath or anosmia) at 3, 7, 10 and 14 days following randomization.
  
- The **secondary objectives** are:
  - 1- To determine the effect of hesperidin therapy on the mean number of COVID-19 symptoms at 3, 7, 10 and 14 days following randomization.
  - 2- To determine the effect of hesperidin therapy on the duration of COVID-19 symptoms.
  - 3- To determine the effect of hesperidin therapy on the presence of each individual COVID-19 symptoms at 3, 7, 10 and 14 days following randomization.
  
- The **exploratory objectives** are:
  - 1- To evaluate the effect of hesperidin therapy on the presence of each individual COVID-19 symptoms on a daily basis based on a patient symptoms' diary.
  - 2- To evaluate the effect of hesperidin therapy on COVID-19-related hospitalization, mechanical ventilation and death in the 14 days following randomization.

**PATIENT POPULATION:** Males and females, at least 18 years of age, who have been diagnosed with a COVID-19 infection and have one or more symptoms.

### Inclusion Criteria:

- Covid-19 positive by polymerase chain reaction (PCR) testing;
  
- Participant must be able to evaluate their symptoms and report them in the symptoms' diary;
  
- Patients must be able to take their oral temperature daily with an electronic thermometer provided to them with study materials.
  
- Males and females, at least 18 years of age, capable and willing to provide informed consent;

- Female patient is either not of childbearing potential, defined as postmenopausal for at least 1 year or surgically sterile, or is of childbearing potential and practicing at least one method of contraception and preferably two complementary forms of contraception including a barrier method (e.g. male or female condoms, spermicides, sponges, foams, jellies, diaphragm, intrauterine device (IUD)) throughout the study;
- Patient must have received a diagnosis of COVID-19 infection within the last 48 hours and have one or more symptoms;
- Outpatient setting (not currently hospitalized or under immediate consideration for hospitalization);
- Patient must be able and willing to comply with the requirements of this study protocol.

Exclusion Criteria:

- Patient currently hospitalized or under immediate consideration for hospitalization;
- Patient currently in shock or with hemodynamic instability;
- Patient undergoing chemotherapy for cancer;
- Patient is unable to take oral temperature using an electronic thermometer;
- Patient who received at least one dose of the COVID-19 vaccine;
- Female patient who is pregnant or breast-feeding or is considering becoming pregnant during the study;
- People taking anticoagulant/antiplatelet medications, those with bleeding disorders, and people two weeks before or after surgery;
- Patient is considered by the investigator, for any reason, to be an unsuitable candidate for the study;
- Regular consumption of natural products containing more than 150 mg of hesperidin or regular consumption of more than 1 glass of orange juice per day;

- Known allergy to any of the medicinal and non-medicinal ingredient: hesperidin, microcrystalline cellulose, magnesium stearate.

**STUDY DESIGN:** This will be a randomized, double-blind, placebo-controlled study. The study will include subjects from Quebec diagnosed with COVID-19 infections. Following informed consent, 216 subjects meeting all inclusion and no exclusion criteria will be randomized to receive either hesperidin 1000 mg once daily (q.d.) or placebo (1:1 allocation ratio) for 14 days. Investigational drug will be delivered to the patients' homes with an electronic oral thermometer and a symptoms diary. Follow-up phone assessments will occur after 3, 7, 10, and 14 days following randomization for evaluation of COVID-19 symptoms. Electronic Case Report Form (eCRF) will be completed by the research personnel over the phone with the patients. The symptoms diary will be mailed back to the coordinating center at the end of the study in a pre-addressed envelope.

**OUTCOMES:**

- The **primary endpoint:**  
Proportion of subjects with any of the following COVID-19 symptoms: fever, cough, shortness of breath or anosmia, at day 3, 7, 10 and 14.
- The **secondary endpoints:**
  - 1- Mean number of COVID-19 symptoms (range 0-13) at day 3, 7, 10 and 14.
  - 2- Duration of COVID-19 symptoms, defined as the number of days between first symptoms and complete disappearance of any symptom.
  - 3- For each COVID-19 symptom listed in the appendix, proportion of subjects with the symptom at day 3, 7, 10 and 14.
- The **exploratory endpoints:**
  - 1- For each COVID-19 symptom listed in the appendix, proportion of subjects with the symptom on a daily basis based on patient-diary.
  - 2- Composite of COVID-19-related hospitalization, mechanic ventilation or death in the 14 days following randomization.

**STATISTICAL RATIONALE AND ANALYSIS:**

Efficacy analysis will be based on the intent-to-treat principle. The primary analysis will compare the proportions of subjects with fever, cough, shortness of breath or anosmia between the two treatment groups using a generalized linear mixed model with terms for treatment group (placebo, hesperidin), time (3, 7, 10 and 14 days) and treatment group x time interaction. The primary analysis will be the comparison between treatment groups at day 7, although treatment groups will also be compared at the other time points. Mean number of COVID-19 symptoms

will be compared between treatment groups using a Student t-test or a Wilcoxon rank-sum test according to distribution. If more appropriate, a Poisson regression model will be used. Duration of COVID-19 symptoms will be compared between treatment groups using a log rank test and Kaplan-Meier curves will be presented. Subjects who will still have COVID-19 symptoms at the end of the study will be censored at the day of their last phone contact or videovisit. The analysis of individual COVID-19 symptoms over time will be similar to the analysis of the primary endpoint and will use generalized linear mixed models. Composite of COVID-19-related hospitalization, mechanic ventilation or death will be compared between treatment groups using a chi-square test. All statistical tests will be two-sided and conducted at the 0.05 significance level. Statistical analysis will be done using SAS version 9.4 or higher.

Using a two-sided 0.05 significance level, sample sizes of 91 in both groups (182 total) will achieve 80% power to detect an absolute between groups difference of 20% in the proportion of patients with COVID-19 symptoms (fever, cough, shortness of breath or anosmia) at day 7, which will be the time point of primary focus. This is assuming that the proportions of patients with the above COVID-19 symptoms at day 7 will be 50% in the placebo group and 30% in the active treatment group. Factoring in a 15% drop out rate, a total of 216 patients will be randomized in the study (108 per group).

A fully independent 3-member Data and Safety Monitoring Board (DSMB) will be established and will review unblinded safety data as detailed in the DSMB charter after randomization of 50 subjects and after randomization of 100 subjects. If necessary, an additional meeting will take place after randomization of 150 subjects. The DSMB charter will pre-specify the rules for early study termination, approved by all board members.

**ANTICIPATED TOTAL NUMBER OF RANDOMIZED PATIENTS:** 216 patients in total will be randomized in this study.

**PHASE:** 2

**STUDY LOCATION:** Canada

## GLOSSARY

ACE2	-	Angiotensin Converting Enzyme 2
AE	-	Adverse event
eCRF	-	electronic Case Report Form
DSMB	-	Data and Safety Monitoring Board
EC	-	Ethics Committee
e-Consent	-	electronic Consent
ICF	-	Informed Consent Form
ICH	-	International Council for Harmonisation
ITT	-	Intent-to-treat
IUD	-	Intrauterine device
IRB	-	Institutional Review Board
LPS	-	Lipopolysaccharides
MHI	-	Montreal Heart Institute
MHICC	-	Montreal Health Innovations Coordinating Center
PCR	-	Polymerase Chain Reaction
qPCR	-	quantitative Polymerase Chain Reaction
PO (po)	-	Per os
PRN	-	pro re nata (as necessary)
SAE	-	Serious adverse event
SOPs	-	Standard operating procedures
SUSAR	-	Suspected Unexpected Serious Adverse Reaction
TESS	-	Treatment-Emergent Signs and Symptoms
WMA	-	World Medical Association

**TIME PERIOD AND NUMBER OF PATIENTS:**

- A. Anticipated Starting Date of Study: 3Q20
- B. Anticipated Completion Date: 4Q20
- C. Anticipated Number of Patients per Site: Centralized recruitment and follow-up
- D. Anticipated Number of Sites: Centralized recruitment and follow-up

Generic Name	Strength and Dosage Form	Therapeutic Classification
Hesperidin	500 mg capsule	Antiviral and immune-modulatory natural product
	Placebo to match 500 mg capsule	NA

## **1 INTRODUCTION**

Emerging viruses are a major threat to human health and the rate at which new pathogenic viruses are emerging has accelerated in the past fifty years. Generally, antiviral drug development has focused on targeting viral components to block virus entry, replication, morphogenesis and propagation, or on the modulation of the host immune response. The frequent outbreaks have highlighted the urgent need for new antiviral treatments.

### **1.1 Background**

#### COVID-19 disease

COVID-19 is due to an infection by the beta-coronavirus SARS-CoV-2 (1). The outbreak of COVID-19 disease started in December 2019 in Wuhan, Hubei Province, China (1,2), has spread to other parts of China and Asia, and is now a pandemic that has reached Europe and North America. The number of confirmed cases has reached over 12 507 849, including 560 460 deaths, as of July 12, 2020. Patients initially present with fever with or without respiratory symptoms, but a large number of patients later develop various degrees of pulmonary abnormalities on chest imaging (3). Although the vast majority of patients only have a common, mild form of illness, approximately 15% of the patients fall into the severe group, with requirement of assisted ventilation and oxygenation (3). These patients suffer from acute respiratory distress syndrome. Pathologic findings reveal edema and prominent proteinaceous exudates, vascular congestion, and inflammatory clusters with fibrinoid material and multinucleated giant cells (4).

This single-strand RNA virus depends on angiotensin converting enzyme 2 (ACE2) for its entry into cells (5). ACE2 is primarily produced in Clara cells and type II alveolar epithelial cells (6).

Accumulating evidence suggests that a subgroup of patients with severe COVID-19 might have also a cytokine storm syndrome (7). By blocking virus entry as well as reducing this dysregulated (exaggerated) inflammatory response has been advocated to address the immediate need to reduce the rising mortality (7,8). Therefore, we hypothesize that Hesperidin, by targeting virus entry (binding to ACE2) and by reducing inflammation, may reduce COVID-19 infection and complications in adults at risk or with evidence of acute respiratory distress syndrome.

### **1.2 Background on Hesperidin**

Hesperidin, a flavonoid naturally present in citrus fruits, is a heteroside of a sugar (rutinose) and hesperetin. Hesperidin was discovered in 1828 and is the oldest commercially available

flavonoid produced from citrus fruits. Hesperetin inhibits the enzyme 3CL protease that contributes to SARS-CoV-2 replication (14). Pharmacological modeling further suggests that Hesperetin could interfere with the regional binding domain (RBD) between the spike protein of COVID-19 and its receptor on human endothelial and epithelial cells (ACE2) (15). Furthermore, Hesperidin/Hesperetin has also been shown to have anti-inflammatory effects and to reduce acute lung injury in models of acute respiratory distress syndromes induced by Lipopolysaccharides (LPS) and mechanical injury (16-19). Hesperidin could therefore interfere with three operative pathways of COVID-19 infection: SARS-CoV-2 binding to its lung epithelial cell receptor ACE2, reduction of viral replication by inhibition of 3CL protease and modulation of excessive lung inflammation and injury leading to respiratory failure.

Hesperidin is already readily available in consumer products such as orange juice (150-200 mg per serving) and natural products from citrus extracts (up to 500 mg per dose). These natural products are advertised as “improving capillary fragility”. Hesperidin is also approved by the FDA and EMA as pharmaceutical, food and beverage additive used to provide texture, improve taste and conservation due to its anti-oxidant properties. The FDA issued a Generally Recognized As Safe (GRAS) notice for orange extracts with 85% Hesperidin content to be used in food ([GRA No 796](#)). In human, plasma concentration of hesperetin, the active component of hesperidin, reach up to 2  $\mu\text{M}$  after consumption of 150 mg hesperidin with peaks after 3 hours and with a half-life of 7 hours. Based on safety, preclinical studies, human PK studies, and PK modeling of hesperidin, a dose of 1g BID of hesperidin is recommended for anticipated efficacy (inhibition of SARS-CoV-1 3CLPro: 8  $\mu\text{M}$ ). SARS-CoV-1 has 95% homology with SARS-CoV-2 (21). A number of human studies have been performed with hesperidin and are summarized in the FDA GRAS notice of 2018 ([GRA No 796](#)). There have been no adverse events observed with high dose hesperidin consumption for long periods of time in human subjects. In particular, Demonty et al. studied 204 subjects and found no adverse events after administration of 800 mg daily hesperidin or placebo in capsules for a duration of 4 weeks (22). Hesperidin is accepted for human use alone or as a component of natural products and has been used for centuries in traditional Chinese medicine as it is major product contained in Chenpi (sun-dried tangerine peels).

### 1.3 COVID-19 symptoms

The epidemiological and clinical characteristics of COVID-19 infection were reviewed by the “Institut National de Santé Publique du Québec” and are available in an [online document](#). Based on a metanalysis of 43 studies including 3600 subjects the most frequently reported symptoms were fever in 83.3% (95% CI: 78.4 – 87.7), cough in 60.3% (54.2 -2 – 66.3), fatigue in 38% (29.8 – 46.5%). More recently, studies have reported that a loss of smell (anosmia) was present in 59% of subjects for one study in 1702 non-hospitalized COVID-19 positive subjects and in 85.6% of 417 hospitalized subjects in another study. Other less frequent symptoms include chills,

sore throat, runny nose, shortness of breath, nausea/vomiting, headache, pain (muscular, chest, abdominal, joint etc.), irritability/confusion and diarrhea. There is therefore great variability in the reported prevalence of COVID-19 symptoms and unknown sensitivity and specificity of any single symptom. For the Hesperidin study, a composite primary endpoint of symptoms was therefore determined based on the current guidelines of the government of Canada for clinicians on COVID-19 symptoms and on guidelines for diagnosis of COVID-19 from the Institut National de la Santé Publique du Québec (INSPQ). The Canadian guidelines for clinicians, reviewed on June 18 2020, list the symptoms in three categories as more frequent (> 50%), less frequent (< 50%) and rare (< 10%) (table 1, [available online](#)).

**Table 1. Frequency of COVID-19 symptom according to the Canadian guidelines for clinicians**

More frequent (>50%)	Less frequent (<50%)	Rare (<10%)

 
• Fever (44-91%)
 
• Cough (57-74%)
 
• Shortness of breath (31-63%)
 
• Fatigue (31-70%)
 
• Loss of appetite (39-84%)
 
• Loss of smell and/or taste (54-88%)
 
	
 
• Sputum production (28-33%)
 
• Muscle aches (11-44%)
 
• Chest pain (16-36%)
 
• Diarrhea (5-24%)
 
• Nausea/vomiting (5-19%)
 
• Headache (6-70%)
 
• Dizziness (9-17%)
 
• Sore throat (11-13%)
 
	
 
• Confusion
 
• Runny nose
 
• Fainting
 
• Skin manifestations
 

Note: Symptoms among older adults (65 years of age and older) and those with underlying medical conditions may be atypical or subtle; for instance they may be more likely to present without fever or respiratory symptoms.
		

The guidelines for the diagnosis of COVID-19 from the INSPQ separated symptoms into group A and group B symptoms. The four group A symptoms are fever (of more than 38° C), cough (recent or exacerbation of chronic cough), shortness of breath and anosmia. These symptoms have less inherent subjectivity in their perception and are classified as more frequent in the Canadian guidelines (table 1). The Hesperidin study will use these group A symptoms as a composite primary endpoint. A list of the COVID-19 symptoms as they will be recorded in patients' diary of the Hesperidin trial is presented in appendix E. Although a proportion of SARS-CoV-2 infections may be asymptomatic, the exact proportion remains currently unknown. In symptomatic subjects, the symptoms can become quite severe causing disability and requiring hospitalization.

## **2 STUDY OBJECTIVES**

- The **primary objective** of the study is to determine the effect of hesperidin therapy on the presence of selected COVID-19 symptoms (fever, cough, shortness of breath or anosmia) at 3, 7, 10, and 14 days following randomization.
- The **secondary objectives** are:
  - 1- To determine the effect of hesperidin therapy on the mean number of COVID-19 symptoms at 3, 7, 10, and 14 days following randomization.
  - 2- To determine the effect of hesperidin therapy on the duration of COVID-19 symptoms.
  - 3- To determine the effect of hesperidin therapy on the presence of each individual COVID-19 symptoms at 3, 7, 10, and 14 days following randomization.
- The **exploratory objectives** are:
  - 1- To evaluate the effect of hesperidin therapy on the presence of each individual COVID-19 symptoms on a daily basis based on a patient symptoms' diary.
  - 2- To evaluate the effect of hesperidin therapy on COVID-19-related hospitalization, mechanical ventilation and death in the 14 days following randomization.

### 3 STUDY DESIGN

This will be a randomized, double-blind, placebo-controlled study. The study will include subjects from Quebec diagnosed with COVID-19 infections. Following informed consent, 216 subjects meeting all inclusion and no exclusion criteria will be randomized to receive either hesperidin (1000 mg q.d.) or placebo (1:1 allocation ratio) for 14 days. Investigational drug will be delivered to the patients' homes. In addition, patients will be provided with an oral electronic thermometer as well as a daily symptoms diary (see appendix). Follow-up phone will occur after 3, 7, 10, and 14 days following randomization for evaluation of the occurrence of any trial endpoints or other adverse events. Electronic CRF (eCRF) will be completed by the research personnel over the phone with the patients.

#### 3.1 Study Schedule

The schedule of visits for this study is outlined in Table 1. However, a patient may be evaluated at any time for safety concerns.

#### 3.2 Enrollment

Informed consent will be obtained from patients who volunteer to participate in the study prior to the conduct of any study-specific procedures. The patient will be considered "enrolled" into the study at the time an informed consent is provided.

### **3.3 Screening Evaluations and Randomization**

Screening evaluations will include a review of the patient's medical history and assessment of concomitant medications to determine if the patient qualifies for the study. Patients who meet all inclusion criteria and no exclusion criteria will be randomized to receive the study product or placebo. All patients must be randomized within 2 days of the diagnosis of COVID-19 infection.

Women of childbearing potential must have a negative urine pregnancy test result at the time of randomization in order to qualify. Qualifying patients will be randomized to receive placebo or hesperidin 1000 mg/day administered in a blinded manner. Blinded randomization will be performed through a system of envelopes. 108 patients will be randomized to active treatment and 108 patients will be randomized to placebo for a total of 216 randomized patients.

### **3.4 Active Treatment Period**

All patients will receive study medication per os (PO) once daily for 14 days. If a dose is missed, it should not be replaced. Throughout the study, patients will undergo phone contacts (at 3, 7, 10 and days to assess for potential study endpoints and other adverse events (AEs). Patients will be dispensed study medication for the 14 days, an electronic thermometer and a daily symptoms diary. At each phone contact, patients will be 1) questioned about COVID-19 symptoms; 2) questioned in a non-specific manner for the occurrence of AEs and any change in concomitant medications; and 3) encouraged to comply with the study protocol including adherence to study medication and completion of the daily symptoms diary.

Please refer to Table 1 and Appendix A for Timetable of Visits and Procedures.

**Table 1 Timetable of Visits and Procedures**

Visits	1. Screening / randomization (Phone call)	2. Contact Point (Phone) –no window**	3. Contact Point (Phone) (± 1 day)	4. Contact Point (Phone) (± 3 days)	5. Contact Point (Phone call) (± 3 days)
Days	0	3	7	10	14
Informed consent	X				
Demographics	X				
Medical/Surgical history	X				
Review concomitant medication	X	X	X	X	X
Covid-19 symptoms (including date of onset)	X	X	X	X	X
Review Inclusion/Exclusion criteria	X				
Urinary pregnancy test*	X				
Randomization	X				
Record potential study endpoints and other AEs		X	X	X	X
Study medication dispensing	X				
Study medication compliance		X	X	X	X

\*For women of childbearing potential

\*\* If day 3 occurs on the weekend, contact point will be done on previous Friday or following Monday, whichever is closer to day 3.

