## **5 STUDY METHODOLOGY**

### **5.1 Efficacy Outcomes**

- The **primary endpoint**:  
Proportion of subjects with any of the following COVID-19 symptoms: fever, cough, shortness of breath or anosmia, at day 3, 7, 10 and 14.
- The **secondary endpoints**:
  - 1- Mean number of COVID-19 symptoms (range 0 – 13) at day 3, 7, 10 and 14.
  - 2- Duration of COVID-19 symptoms, defined as the number of days between first symptoms and complete disappearance of any symptom.
  - 3- For each COVID-19 symptom listed in the appendix, proportion of subjects with the symptom at day 3, 7, 10 and 14.

Duration of symptoms will be determined as follows:

- If randomization and study product reception by participant occur the same day, first day of symptoms will be defined as the day of randomization;
- If randomization and study product reception by participant occur on different days, first day of symptoms will be defined as the day of study product reception.

- The **exploratory endpoints**:
  - 1- For each COVID-19 symptom listed in the appendix, proportion of subjects with the symptom on a daily basis based on patients' diary.
  - 2- Composite of COVID-19-related hospitalization, mechanic ventilation or death in the 14 days following randomization.

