### **5.3 Withdrawal of Patients from the Study**

Patients have the right to withdraw from the study at any time during the course of the study. However, every effort should be made, within the bounds of safety, patient choice and the provisions of informed consent, to have each patient complete the study up to and including the last protocol-specified phone call at Day 14. If the study medication jeopardizes the patient's health or if the patient wishes to discontinue for any reason, study medication can be discontinued but the patient should be encouraged to remain in the study for the follow-up phone calls up to Day 14. Patients who are not compliant during the active treatment period should be counseled on the importance of complying with study requirements and be allowed to remain in the study. No patient who has withdrawn his/her consent from the study during the active treatment period should be replaced.

In the case of an adverse event or safety concern, the study medication may be withheld temporarily, or the dose reduced, as per investigator judgment. Investigators should discuss the patient condition with the MHICC medical monitor in order to determine the appropriate dose reduction algorithm or study medication discontinuation plan.

Patients withdrawn at any time from the study during the active treatment period should complete all last protocol-specified phone call assessments at Day 14 (the reason for withdrawal from the study, the date of the last videovisit/phone call and the date of the last dose of double-blind medication will be clearly documented in the eCRF).

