#### **5.4 Study Completion**

The study will end when the last randomized patient will have completed his (or her) 14-day follow-up phone contact or videovisit. Completion of the study by a patient should be clearly indicated in the eCRF, along with the date of the last phone call and the date of the last dose of double-blind medication.

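### The last scheduled call may be made on Day 11 to 13 with none after it, so active questioning about 14-day events and adverse events can stop 1 to 3 days early

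*Protocol*

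**What the plan says.** **Timing of the last contact.** Protocol Table 1, repeated in SAP Appendix B, heads the final column "5. Contact Point (Phone call) (± 3 days" with a target of Day 14. Protocol 5.3 asks that patients "complete the study up to and including the last protocol-specified phone call at Day 14". Protocol 5.4 adds: "The study will end when the last randomized patient will have completed his (or her) 14-day follow-up phone contact or videovisit". No contact is scheduled after that one. Protocol 3.1 permits an unscheduled evaluation for safety but does not plan one for everybody.

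**Events and adverse events.** Protocol 5.1 lists as an exploratory endpoint the "Composite of COVID-19-related hospitalization, mechanic ventilation or death in the 14 days following randomization". SAP 4.3 takes these events from the Adverse Events Form. SAP 6.4.3 divides the number of subjects with an event by the number randomized to the group, with no censoring at last contact. Protocol 5.2.1 collects adverse events at the four calls. Treatment is once daily for 14 days (Protocol 3.4), taken at bedtime (Protocol 6.2).

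**Exposure.** Protocol 5.4 wants the last-dose date recorded at completion. SAP 6.5.1 computes exposure from it.

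**Symptoms.** The patient keeps a diary for 14 days (Protocol Appendix E) and mails it back at the end (Protocol Synopsis, Study Design). SAP 4.1 and 4.2 define the symptom endpoints by diary day, using the eCRF symptoms form. The Synopsis also states: "Electronic Case Report Form (eCRF) will be completed by the research personnel over the phone with the patients".

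**The concern.** A patient can be handled exactly as the schedule allows and still have the last contact on Day 11 of a 14-day observation period. Nobody is then scheduled to ask whether the patient was hospitalized, ventilated or died on Days 12 to 14, or had an adverse event under the last doses. The diary does not fill that gap. It is a symptom checklist with a temperature line and one comment line, and has no field for hospitalization, adverse event severity or relationship to study drug.

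The consequence for the composite is specific. With all randomized subjects in the denominator and no censoring, an unreported late event becomes a recorded non-event instead of a missing value. For safety, the end of treatment is the part least well covered. For exposure, a last-dose date is needed before the last dose has been taken.

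**Working it through.** **1. The plan's own figure.** The sample size concerns Day 7 (Protocol 8.1, SAP 6.1): 50% against 30%, two-sided 0.05, 80% power. With unpooled variance, n = (0.5 × 0.5 + 0.3 × 0.7) × (1.960 + 0.842)² / 0.20² = 90.26, so 91 per group. With 15% dropout, 91 / 0.85 = 107.1, so 108 per group and 216 in total. The plan's figures are reproduced. They do not depend on the last-call window.

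**2. Days of the 14-day window left after the last call.** Gap = 14 − call day, with call days from 14 − 3 = 11 to 14 + 3 = 17.

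| Last call | Days left | Share of 14 days |
|---|---|---|
| Day 11 | 3 | 21.4% |
| Day 12 | 2 | 14.3% |
| Day 13 | 1 | 7.1% |
| Day 14 to 17 | 0 | 0% |

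**3. Range over all patients.** The documents do not say how calls fall within the window. If none is early, the loss is 0. If every call were on Day 11, it would be 3/14 = 21.4% of the follow-up days. If calls were spread evenly over the seven days (an assumption), 3/7 = 43% would be early, and the mean gap over all patients would be (3 + 2 + 1)/7 = 0.86 days, or 0.86/14 = 6%.

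**4. Doses taken after the last call.** With the first dose at bedtime on Day d, the fourteenth is on Day 13 + d. The doses on or after the evening of a call on Day c number 14 + d − c.
- First dose on Day 0, call on Day 11: 14 + 0 − 11 = 3 doses.
- First dose delayed by 1 to 3 days (assumed; Protocol 5.1 foresees later delivery but gives no length), call on Day 11: 4 to 6 doses.
- Call on Day 14 with a delay of 0 to 3 days: 0 to 3 doses.

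**5. Effect on exposure.** SAP 6.5.1 uses last dose − first dispensing + 1. Suppose dispensing and first dose are on Day 0 and a Day 11 call records the Day 10 dose as the latest. Exposure is then 10 − 0 + 1 = 11 days, against 13 − 0 + 1 = 14 if treatment is completed. In the SAP's three-day categories, that moves the patient from 13–15 to 10–12.

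**6. Symptoms.** If the diary is completed, returned and entered, no symptom day is lost, whatever the call date. If the eCRF is filled only during calls, a last call on Day 11 leaves Days 12 to 14 empty. SAP 6.2.1 does not impute a day on which all symptoms are missing (except before a death), so Day 14 would be missing. The documents do not say which of these applies.

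**The case against.** **The diary covers symptoms.** A reader might infer that Day 14 symptoms are unobserved after an early call and that symptom duration is censored at that call. The documents do not support this. The diary runs for 14 days and is mailed back, and the SAP, which overrides the protocol where they differ, works by diary day and censors at the last assessment. What stands is only the unstated route from later diary days to the eCRF.

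**Events can still become known.** Calling late events unobserved would be too strong. Serious adverse events that become known are reportable, study endpoints go into the eCRF within 5 days of awareness (Protocol Appendix B 4.2), and unscheduled evaluation is possible. The same appendix limits other adverse events on the eCRF to those judged related and to clinically significant laboratory abnormalities, so the safety loss is smaller than a count of all adverse events would suggest. This stands in part, because these routes are passive and depend on someone reporting. The reporting period also differs between Protocol 5.2.1.1 (14 days) and Protocol Appendix B and SAP 5.2 (21 days), and those passages must be reconciled.

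**Other windows.** Day 7 ("3. Contact Point (Phone) (± 1 day") and Day 10 ("4. Contact Point (Phone) (± 3 days") are also two-sided, and a weekend Day 3 call moves to the "contact point will be done on previous Friday or following Monday, whichever is closer to day 3". A reader might see the same fault there. But a later call can read those diary days and ask about events since the previous one, so no lost data are shown.

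**Size.** The composite is exploratory and the arms are blinded, so missed events would be expected to fall similarly on both. This stands, and keeps the point modest.

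**Conclusion.** The concern holds in a limited form. The schedule allows active ascertainment of composite events and adverse events to end 1 to 3 days (7% to 21%) before the 14-day window closes. Unreported composite events after an early call count as no event. The last-dose date is unavailable at that call for patients still on treatment. How later diary days enter the eCRF is unspecified.

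The per-patient figures need only day arithmetic. The number of patients affected cannot be derived from the documents. It would be wrong to read 43% as an estimate, since that holds only if calls are spread evenly, whereas the text targets Day 14. The Day 7 comparison and the 216 patients are untouched. This is a cheap improvement of modest impact and does not threaten the trial's main conclusion.

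**What to change.** - In Protocol Table 1 and SAP Appendix B, set the window of the last call to 0 to +3 days. The uncovered part of the 14-day event window falls from at most 3 days to 0.
- State that this call asks about composite events and adverse events through Day 14 and records the last-dose date.
- State that all diary days through Day 14 are entered in the eCRF, including from the mailed diary where needed.
- Leave the Day 3, Day 7 and Day 10 windows as they are.

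The number of calls and patients does not change. The cost is a wording change in two tables and slightly less scheduling freedom. One gap remains: where delivery was late, some doses may still follow a Day 14 call (0 to 3 under the assumed delay of 0 to 3 days).
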